10.9. Sensitivity Analyses

Sensitivity analyses will be conducted as follows:

- Excluding those who have admissions/costs in the top 1% of all participants
- Excluding participants who resided in the same household as another participant.
- We will also conduct a complete case analysis to examine the effects of the missing data, where relevant (ie. Self-reported outcomes).

11. Interaction between intervention arms

Given the factorial design of the trial, we will assess for multiplicative interaction. Because each of our two interventions was designed to address very different patient barriers to

medication adherence (financial barriers vs. Knowledge/motivation), we don't anticipate major multiplicative interaction effects.

12. Health Economic Analysis

The primary outcome will be mean total 3-year in-study health care costs for patients receiving copayment elimination (or not) and those receiving MOXIE (or not), adjusting for co-intervention received. We will include costs for hospitalization and ED visits, physician claims (specialist and primary care physician visit and procedure billing costs), prescription medications (including those subject and not subject to copayment elimination), nonphysician ambulatory costs (day medicine and day surgery clinics), and outpatient diagnostic imaging and laboratory costs. The total costs will be calculated as the sum of these costs. Alberta Health uses Canadian Institute of Health Information case-mix grouper methods to estimate hospital costs and ambulatory-case costing methods to estimate outpatient costs.

Physician claims will be based on the amount paid by Alberta Health. The cost of medications will be estimated by combining a database containing a comprehensive list of medications dispensed to all Alberta residents with a price list from Alberta Blue Cross, including dispensing fee. Diagnostic imaging and laboratory costs will be based on estimates provided by Alberta Health Services. All costs will be reported in 2021 Canadian dollars.

Assuming a non-gaussian distribution of costs, we will use established methods to enable comparisons of mean total costs, as these are easily interpretable and relevant to health care payer. We will use non-parametric bootstrap estimates to derive standard deviations and 95% confidence interval (95% CI) and mean cost differences between the treatment arms as we have done. We will use 1000 bias-corrected bootstrap replications, and sample with replacement from the original data, we will estimate the distribution of a sampling statistic to derive 95% confidence intervals. To allow us to control for stratified variables (age ≤ 70 ; sex and low-income status), we will also use generalized linear models to compare total costs across groups, using a gamma distribution and log-link function.

13. Statistical Software

We will conduct all the analyses using SAS software, version 9.4 (SAS Institute Inc, Cary, North Carolina), and Stata, version 17 (Stata Corp, College Station, Texas).

14. Differences to the protocol

None

15. References

1. Mirolla M. THE COST OF CHRONIC DISEASE in CANADA EXECUTIVE SUMMARY. 2004;

7. Mortality, Summary List of Causes. 2008; Available from: www.statcan.gc.ca,
8. Health Agency of Canada P. Leading Causes Of Hospitalization, Canada, 2009/10; Available from: www.publichealth.gc.ca

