4.6. Timing of outcomes as assessments

The primary outcome data was ascertained through administrative health data held within the province of Alberta, including linked datasets such as: laboratory data, pharmacy dispensation data, acute care data, outpatient physician claims data, and demographic data. Participants were followed for a minimum of 2.5 years from the time of randomization through until March 30, 2021. This data will be available as of early 2022.

Self-reported outcome measures were obtained via electronic and paper-based surveys which were sent to participants 6-, 18-, and 33-months after randomization.

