6.1. Primary outcome

Record of any of the following identified within the Discharge Abstract Database will be counted as one primary outcome. The number of composite outcomes will be used; therefore, any one individual may have multiple outcomes within the observation window.

The rates of the composite outcome will be calculated by generating the observation time, defined as the period from randomization to study completion, taking into consideration censoring for death or outmigration.

Outcome	Description	Classification Source	Codes included	Exclusions	Source
Myocardial Infarction	Acute myocardial infarction Subsequent myocardial infarction	ICD-10	I21.X I22.X	None	Quan et al. (38), Austin et al. (39)
Stroke	Central retina artery occlusion Cerebral infarction Stroke, not specified as hemorrhage or infarction Intracerebral hemorrhage Subarachnoid hemorrhage Transient cerebral ischemic attacks	ICD-10	H34.1 I63.X I64.X I61.X I60.X G45.X	None	Kokotailo and Hill (40)
Coronary Revascularization	Coronary Angioplasty Coronary endarterectomy/excision Coronary local pharmacotherapy	Canadian Classification of Health Interventions (CCI)	1.IJ.50 1.IJ.57 1.IL.35 1.IJ.76		CIHI

	Coronary Artery Bypass				
Death	Death (all-cause)	Vital Statistics			
Ambulatory Care-Sensitive Hospitalization for Diabetes	Type 1 DM with coma Type 1 DM with acidosis Type 1 DM with hypoglycaemia Type 1 DM without (mention of) complication Type 2 DM with coma Type 2 DM with acidosis Type 2 DM with hypoglycaemia Type 2 DM without (mention of) complications Other specified DM with coma Other specified DM with acidosis Other specified DM with hypoglycaemia Other specified DM without (mention of) complication Unspecified DM with coma Unspecified DM with acidosis Unspecified DM with hypoglycaemia Unspecified DM without (mention of) complication	ICD-10	E10.0^^ E10.1^^ E10.63 E10.9^^ E11.0^^ E11.1^^ E11.63 E11.9^^ E13.0^^ E13.1^^ E13.63 E13.9^^ E14.0^^ E14.1^^ E14.63 E14.9^^	None	CIHI

Outcome	Description	Classification Source	Codes included	Exclusions	Source
Ambulatory Care-Sensitive	Type 2 diabetes mellitus with ketoacidosis		E11.10 E10.10	None	Gao et al. (41)

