10.4. Analysis Methods- Primary Outcome

Consistent with an intention-to-treat analysis, we will categorize all participants by their randomization group, regardless of compliance (intention-to-treat), in our primary analysis. For those participants who are no longer actively receiving the self-management intervention or completing follow-up surveys, as permitted by CHREB, we plan to use available health administrative data until the time of death or outmigration from the province.

A Poisson model will test the main effects of the impact of the interventions on the rate of the primary outcome. This technique was chosen as individuals may experience multiple outcomes prior to the end of the study period, therefore we will account for both number of events and varying observation time within the Poisson model (by using an offset to account for losses to follow-up). The likelihood ratio test will test a negative binomial regression model within the Poisson model to examine for the presence of overdispersion. If present, negative binomial models will be used.

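### The 3-year cost outcome is formed from follow-up guaranteed for only 2.5 years, with no adjustment for incomplete cost totals; the effect is small

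*Combined protocol and SAP*

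**What the plan says.** All references are to the combined protocol and SAP unless stated otherwise.

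- **Outcome (section 12).** "The primary outcome will be mean total 3-year in-study health care costs for patients receiving copayment elimination (or not", and likewise for the education intervention. The total is a plain sum of components: "The total costs will be calculated as the sum of these costs".
- **Follow-up (section 4.6).** "Participants were followed for a minimum of 2.5 years from the time of randomization through until March 30, 2021".
- **Cost methods (section 12).** "We will use non-parametric bootstrap estimates to derive standard deviations and 95% confidence interval (95% CI) and mean cost differences between the treatment arms". To control for the stratification variables, "we will also use generalized linear models to compare total costs across groups, using a gamma distribution and log-link function". Neither description mentions exposure time, an offset, a weight, annualisation or imputation.
- **Clinical primary outcome, for contrast.** Section 6.1 computes observation time "taking into consideration censoring for death or outmigration". In section 10.4, "we will account for both number of events and varying observation time within the Poisson model", which is done "by using an offset to account for losses to follow-up". These provisions are written for the event rate only.

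**The concern.** A 3-year total cannot be observed for everyone when entry is staggered and follow-up ends on one calendar date less than 3 years after the last entry. Anyone randomized after 30 March 2018 is cut off before month 36, and anyone who leaves Alberta stops generating provincial records. The plan allows for unequal observation time in the event-rate analysis but carries no equivalent into the cost analysis. Followed as written, section 12 treats partial totals as complete ones.

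At stake is the level of the reported mean, which section 12 itself says was chosen for its relevance to the payer, and to a lesser degree the absolute difference between arms. The window is also not pinned down: section 12 does not state that costs stop at month 36 for early entrants, some of whom have more than 5 years of data.

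**Working it through.** **The plan's own 3-year figure.** The cost outcome has no power calculation. The only calculated figure that uses 3 years is the sample size in section 4.8. The Signorini Poisson formula with rate 0.14 per year, rate ratio 0.88, two-sided 5% alpha (sidedness assumed) and 80% power gives

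N = (1.960·√4 + 0.842·√(2 + 2/0.88))² / (3 × 0.14 × (ln 0.88)²) = 4667,

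and 4667 × 1.01 = 4714. Both match the plan. Two things follow. Three years is an *average* follow-up assumption there, not a window that everyone completes. And although section 4.8 states a loss of 1% per year, the inflation applied is 1% once, so the out-migration rate can be read two ways.

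**Inputs.** Closure is 30 March 2021 (4.6). Enrolment lasted 30 months, with calls from November 2015 (7.1). Out-migration is 1% per year, or 1% in total (4.8; section 5.6 of the later SAP calls it annual). Uniform accrual is my assumption, because the documents give no accrual curve.

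**Closure alone.** If potential follow-up is uniform from a to b years, with a < 3 < b:

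- share cut short = (3 − a)/(b − a)
- missing share of the 3-year window = (3 − a)² / [2(b − a)] ÷ 3

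| Entry period | a | b | Cut short | Window missing |
|---|---|---|---|---|
| 1 Nov 2015 to 30 Apr 2018 | 2.916 | 5.410 | 3.4% | 0.05% |
| 1 Nov 2015 to 31 May 2018 | 2.831 | 5.410 | 6.6% | 0.18% |
| 1 Nov 2015 to 30 Sep 2018 | 2.497 | 5.410 | 17% | 1.4% |
| 30 months ending 30 Sep 2018 | 2.5 | 5.0 | 20% | 1.7% |

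The first two rows take 30 months from the first calls. The last two take the 2.5-year minimum as attained. For one participant, the most that closure can remove is 0.5/3 = 16.7% of the window.

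**Out-migration alone.** With a constant rate r, the missing share is 1 − (1 − e^(−3r))/(3r). At 1% per year this is 1.5%. At 1% over the whole 3 years (3r ≈ 0.01) it is about 0.5%.

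**Together.** The low end is 0.05% + 0.5%, or about 0.5%. At 1% per year, the first row gives 1.5%, the third 2.9% and the fourth 3.1%.

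**Back-loaded accrual.** Section 7.1 reports that the initial recruitment plan fell short and the timeline was extended, so late-weighted entry is plausible. With linearly rising accrual to 30 September 2018, 32% are cut short and 2.7% of the window is missing, or 4.1% with 1% per year out-migration. Ending in April–May 2018, the same pattern gives 7–13% cut short and 1.6–1.8% missing including out-migration.

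**Effect on the estimates.** If cost per year is constant within arm and a share m of the window is missing in both arms, means μ₁ and μ₀ become (1 − m)μ₁ and (1 − m)μ₀. The difference becomes (1 − m)(μ₁ − μ₀), which is closer to zero whatever its sign. The ratio μ₁/μ₀ is unchanged.

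**The case against.** **The size is minor and the comparison is protected.** Closure is a calendar event and independent of randomized arm. Cost is a secondary outcome (4.4), and section 5.2 treats secondary outcomes other than the components of the primary as exploratory. This stands, and it is why the point concerns specification and a modest bias in level. Only out-migration could differ by arm, and the documents give no sign that it does.

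**The minimum is a floor.** If enrolment began with the November 2015 calls and lasted 30 months, the shortest follow-up is about 2.8–2.9 years, which is consistent with section 4.6. This also stands. The 17–20% figure applies only if the last entry was near September 2018.

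**Section 10.3 covers loss to follow-up for secondary outcomes.** It does so in general terms, but it is framed around self-reported data and mentions neither costs nor calendar closure. The established methods cited in section 12 concern non-Gaussian costs. Treating partial totals as complete is not stated outright in the plan; it follows from summing costs and analysing them with no exposure term. I would not rely on section 10.3 to fill the gap.

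**Costs after leaving Alberta may not be the payer's costs.** This is arguable, given the payer framing in section 12. On that reading only closure matters, and the missing share falls to about 0.05–1.7% under uniform accrual. The plan should say which reading applies.

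**A stronger reading to resist.** Because section 12 calls the costs *in-study*, a reader might infer that they run to March 2021 for everyone. Uniform potential follow-up of 2.5–5.0 or 2.9–5.4 years averages 3.75 or 4.15 years, so totals would be 25% to 38% above a 3-year figure (3.75/3 and 4.15/3), before deaths and out-migration. That requires *in-study* to override *3-year* in the same phrase. The text does not support it as an error, only as a reason to state the cut explicitly.

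**Conclusion.** The point holds as a gap in the cost analysis with a small effect. The stated 3-year total is not observable for everyone, and neither cost method allows for that. Under uniform accrual, closure cuts short about 3–7% of participants (entry ending April–May 2018) to 17–20% (last entry September 2018). About 0.5–3% of 3-year person-time is missing including out-migration, and somewhat more if accrual was back-loaded. At constant cost per year, mean costs are understated by about that share.

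A reader might infer that the treatment comparison is biased in a known direction, for instance that the cost difference is too low. The documents do not support that. Balanced closure tends to attenuate the absolute difference, and a saving would shrink as well as an excess. If the difference accrues unevenly over the 3 years, the direction depends on its timing. The cost ratio from the log-link model is little affected.

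Nor are deaths part of the problem: cost after death is truly zero, so those totals are complete.

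The size rests on assumed accrual, on the reading of the out-migration rate, and on roughly constant cost over time.

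**What to change.** 1. State in section 12 that costs are counted from each participant's randomization and cut at month 36. Give the actual last randomization date, which settles the scale of the problem.
2. Estimate the 3-year means and their difference with a partitioned inverse-probability-of-censoring weighted estimator. Treat closure and out-migration as censoring and death as complete, and use the same weights in the bootstrap and the gamma model. If costs after leaving the province are deliberately outside the payer's perspective, say so and treat only closure as censoring.
3. Add a sensitivity analysis in participants whose randomization date allows a full 36 months (on or before 30 March 2018). Selecting on entry date, not on observed follow-up, keeps the randomized comparison.

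Alternatively, use a 30-month window and label it as such. This removes the closure problem but not out-migration: at 1% per year, 1 − e^(−0.025) ≈ 2.5% of participants would still be incomplete, so weighting for that is still needed.

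The cost is wording, modest programming and slightly wider intervals, or loss of the last six months of cost data under the 30-month option. No new data are needed. The introduction to the later SAP already cites a cost result, so if the analysis is finished, the window actually used should be reported and the weighted estimate added as a sensitivity analysis.

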Cost-related barriers to medication adherence are relevant in Canada: While the Canadian publicly funded health care system funds hospital and physician care, patients are responsible for many of the direct costs related to outpatient management of their chronic conditions. Canada is unique among OECD countries given that not all citizens have insurance coverage for outpatient medications (14,15), and even those with supplemental insurance are usually subject to cost-sharing (i.e., copayments or deductibles) (16). This requires that patients pay a portion of the cost at the time of medication dispensing; typically a copayment of 20-30% of the total cost of the prescription (17) or deductibles which may be as high as 5-20% of household income (18). This may represent a substantial financial barrier, since our recent survey noted that 64% of patients with chronic diseases had an annual household income <\$55,000 (16). Furthermore, we found that the average self-reported annual out of pocket expenses on medications was \$782 (95%CI \$668-\$897). In Alberta, government-sponsored drug insurance is provided to people on social insurance and those aged over 65. People who do not meet age or income criteria can pay a premium to receive the government insurance. All Albertans over age 65, and those who pay a premium to receive Blue Cross coverage pay 30% copayment for drugs.

While copayments are meant to reduce inappropriate medication use, they may have important negative consequences. Being faced with costs at the time of medication dispensing may discourage patients from filling prescriptions, including for important preventive medications. Recent Canadian studies estimated that up to 10% of people experienced cost-related medication non-adherence (19), and that 23% of Canadians with chronic conditions have either skipped medication or failed to fill a prescription due to cost (20). In our recent survey of Western Canadians with chronic diseases, 8-20% identified financial barriers to drugs; and patients with these barriers were 30-55% less likely to use statins (16). Studies suggest that reducing copayments can improve adherence, though the impact on clinical outcomes is uncertain. One way to reduce the impact of these cost barriers is to provide full coverage for “high-value” medications (i.e., *defined as those medications that have been shown to confer important benefits in high quality studies, and/or provide good value for money*).

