Secondary Objectives:

To determine the effect of two novel interventions on medication adherence, overall quality of life, and health care costs.

4. Trial Methods

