4.2. Trial Interventions

- 1. Elimination of copayments:** (reduction from 30% to 0%) for select high-value preventive medications by enrolling patients in a new Alberta Blue Cross drug coverage plan which was designed by the study team, including leaders at Alberta Health specifically for ACCESS (see letter of support, [name]). Since these patients either have or are at high risk of cardiovascular disease, the medications include statins, beta blockers, ACE-inhibitors, angiotensin receptor blockers, calcium channel blockers, diuretics, anti-platelet agents,

anticoagulants, oral hypoglycemics, insulin and smoking cessation aids (23) (see Appendix II). These formulary changes will be operationalized by transferring patients allocated to this intervention to a new government-sponsored Alberta Blue Cross formulary plan with updated payment rules.

2. **Patient education strategy on lifestyle modification and medication use** designed in collaboration with a leading marketing firm (see letter of collaboration, Emergence) and based on our recent survey of Western Canadians (3,4,24). The education program will be combined facilitated relay of information on patient medication use to their health care provider. Patients who are not using guideline-recommended therapy (including statins) at baseline will be given personalized recommendations to take to their usual clinician, aiming to increase the appropriate use of beneficial medications. Dissemination will occur by email invitations to access the personalized study website portal or regular post, depending on preferences of the participant (elicited at baseline). Personal health information will not be sent within emails. For any educational messages tailored to a specific patient's health information (as provided by them within baseline information forms), patients will be directed to log on to a secure password protected website.

Control patients for the two intervention arms will continue to receive all medications as per their usual coverage and/or will receive annual mailings of general educational materials about chronic disease.

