4.4. Secondary Outcomes

- 1) each individual component of the primary endpoint
- 2) medication adherence for selected medications as defined below
- 3) overall quality of life as measured by the Euroqol EQ5D-5L
- 4) the cost of the interventions and other costs relevant to the health care system assessed in a concurrent economic evaluation.

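### Section 12's total cost has no intervention-cost item and prices drugs by one list for everyone, so as written it does not give the payer's net cost of either intervention

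*Combined protocol and SAP*

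**What the plan says.** All references are to the combined protocol and SAP unless stated.

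- Section 4.4 lists as the fourth secondary outcome "the cost of the interventions and other costs relevant to the health care system assessed in a concurrent economic evaluation".
- Section 12 sets mean total cost over three years as the economic primary outcome, compared by assignment to each intervention. The components are hospital and emergency care, physician billing, prescription drugs (covered by the waiver or not), non-physician ambulatory care, and imaging and laboratory tests. It then closes the list: "The total costs will be calculated as the sum of these costs".
- For drugs, Section 12 combines dispensing records "with a price list from Alberta Blue Cross, including dispensing fee". It makes no distinction by assignment and no split between plan and patient. Physician claims, in the same paragraph, are costed at what Alberta Health paid.
- Section 12 justifies comparing mean costs "as these are easily interpretable and relevant to health care payer".
- Section 4.2 describes the copayment on selected drugs falling from 30% to 0% through transfer to a new government-sponsored plan. It describes an education programme designed with a marketing firm and delivered by post or secure website, with personalised recommendations for participants not on guideline therapy.
- Section 14 records no differences to the protocol.

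**The concern.** The outcome list promises the cost of the interventions, and the analysis section defines a total that has no place for it. Nothing in Section 12 covers designing, mailing, hosting or running the education and relay programme. The waiver is itself a change in who pays for covered drugs, and a costing rule that prices each dispensing identically in both arms cannot show that change.

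At stake is what a payer would conclude. The Section 12 contrast could show no added cost, or a saving, when the payer's own outlay has risen. Bootstrap intervals and the gamma model do not help, because the missing amounts are absent from the quantity being modelled.

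**Working it through.** The plan states no cost, cost difference or power for costs, so there is no figure of its own to reproduce. The check is an accounting identity followed by an illustration.

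**Copayment contrast.** Let D be the list-price cost of covered drugs per participant over three years under usual coverage, and u the relative rise in covered-drug use caused by the waiver.

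- Section 12 drug difference, with one price list for all: D(1 + u) − D = uD.
- Payer's drug difference, with 70% borne under usual coverage and 100% under the waiver: D(1 + u) − 0.70D = (0.30 + u)D.
- Omitted from the payer's view: 0.30D, whatever the value of u.

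At u = 0, Section 12 shows a drug difference of zero while the payer's covered-drug spending goes from 0.70D to D, a rise of 0.30/0.70 = 43%.

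If the waiver also saves an amount S in other care, Section 12 shows a net saving once S exceeds uD, but the payer saves only once S exceeds (0.30 + u)D. Between these two values the sign is wrong for the payer.

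**Size (illustration).** Section 2 says of a survey: "we found that the average self-reported annual out of pocket expenses on medications was" $782 (95% CI $668 to $897). Assume that a share s of this is the 30% copayment on covered drugs. Then 0.30D = 3 × 782 × s, and D = 3 × 782 × s / 0.30. The documents give no value for s or u.

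| s | D | 0.30D (range from survey CI) | Section 12 drug difference, u = 5% | Payer's drug difference, u = 5% |
|---|---|---|---|---|
| 0.25 | $1,955 | $587 ($501 to $673) | $98 | $684 |
| 0.50 | $3,910 | $1,173 ($1,002 to $1,346) | $196 | $1,369 |
| 1.00 | $7,820 | $2,346 ($2,004 to $2,691) | $391 | $2,737 |

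(Rows may differ by $1 from rounding.) In the middle row, any saving in other care between $196 and $1,369 would appear as a net saving in Section 12 and be a net cost to the payer.

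**Education contrast.** Let E be programme delivery cost per participant; the documents give no figure. Section 12 omits E. A small offset runs the other way. If education raises covered-drug use by a fraction v, gross pricing books vD, but the payer bears only 70% of it in the half of participants without the waiver, so 0.85vD overall (ignoring product terms in u and v). The net shortfall is E − 0.15vD. With s = 0.50 and v = 5% (assumptions), the offset is 0.15 × 0.05 × 3,910 = $29.

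**The case against.** The strongest reply is that no payer perspective is declared. The objective is "To determine the effect of two novel interventions on medication adherence, overall quality of life, and health care costs", and the remark about the payer in Section 12 is a reason for comparing means when costs are skewed. From a view that adds system and patient spending, a copayment is a transfer, and pricing every dispensing alike is legitimate. This stands, and it is why the gross total should be kept. It does not supply the missing programme cost, which is absent under any perspective.

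Second, pricing at full list in every arm is an inference: the text does not say whether patient shares are netted out. It is the natural reading, because one rule is given for everyone and no split is mentioned.

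Third, a reader might infer that the waiver never enters total cost, or that both interventions are treated as costing the payer nothing. Neither follows. The 30% share is counted in both arms and only the transfer cancels; extra use under the waiver is captured. Nor does it follow that the cost question cannot be answered. Section 4.4 names intervention cost as an outcome, so it could be reported separately, and the payer's drug cost can be derived from the list price and the 30% rule.

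Fourth, the SAP introduction reports that the waiver did not reduce health care costs. Adding cost to the waiver arm would not reverse that statement, but it also does not tell a payer whether costs rose.

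Fifth, the $782 is self-reported survey spending on all medications, under varied coverage, and is not trial data. This also stands; the figure shows scale only.

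**Conclusion.** The point holds in this form: as written, the Section 12 total does not give the payer's net cost of either intervention, and it does not say how the intervention cost promised in Section 4.4 enters the analysis. For a payer, the copayment contrast is too favourable by 0.30D, and the education contrast by E less a small offset.

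The copayment part rests on the natural reading of the drug-pricing rule and on a 70% plan share under usual coverage, which follows from the 30% copayment in Sections 2 and 4.2. The missing programme cost needs neither assumption. About $590, $1,170 or $2,350 per person over three years corresponds to s of 25%, 50% or 100%; the documents do not support choosing among these or treating the largest as an estimate.

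This should be fixed, but it is not critical to the trial. It concerns one secondary outcome, and the clinical primary outcome is unaffected.

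**What to change.** In Section 12:

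1. State the perspective of each cost analysis.
2. For the payer view, cost covered drugs at the amount the plan pays: list price less the 30% copayment where it applied, and full list price under the waiver.
3. Add the per-participant delivery cost of the education and relay programme to those assigned to it, net of the annual general mailings that Section 4.2 describes for controls.
4. Report the gross list-price total as a second view, labelled as system plus patient.

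If cost results have already been reported, the payer view can be issued as a labelled supplementary analysis.

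The drug part needs only the price list, drug class and assignment. Section 8 lists no plan payment records, so the 30% rule would have to be applied by calculation and stated as an assumption. Programme costs must be compiled from the study's own records, which is the main extra work. The cost results will become less favourable to the interventions.
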